Radiant heat sensitivity assay¹¹: Assay involves determining the sensitivity threshold for painful thermal stimulation. Stimulation is provided with a radiant heat device¹¹. This device uses a focused light beam to slowly heat a subject's skin. Before the start of the training/ experimental trials, subjects will be shown device and allowed to feel the stimulus with their hand. Subject will be asked to rest their forearm or calf on a room temperature glass plate. Using a mirror, the light source will be positioned under a marked area on the subject's forearm or calf. Subjects are told to raise their leg or arm when they feel the stimulus transition from "innocuous warmth or heat" to "painful heat." When the leg or arm is raised from the surface of the glass, the thermal stimulus automatically stops and the time since the beginning of the trial is recorded as "latency to respond." Each trial lasts for a maximum of 20 seconds. The device is set so that typical withdrawal thresholds occur at approximately 10 seconds into the trial. The temperature on the glass at this point is $\sim 47^{\circ}\text{C}$ (121°F). The maximum temperature of the trial at the 20 second cutoff time point is 50°C which is well below the temperature that causes tissue damage in humans. For each limb, two trials will be completed in two distinct marked areas to avoid re-testing at a single site. Total testing time (2 trials on forearm and 2 trials on calf) is < 5 minutes.

A second assay will be used to evaluate the quality and unpleasantness of thermal pain. Each subject will receive a constant 45°C stimulus. 45°C is a standard temperature that is the typical minimal stimulus necessary to feel thermal pain. Stimulus (3cm x5cm heating block) will be applied for 3 seconds. Immediately following stimulus, the subject will be asked to evaluate the intensity and unpleasantness of the pain. This is done with a standard 0-10 visual analog scale (VAS). On the "intensity scale", "0" is represented as "no pain" and "10" is represented as "the worst pain imaginable." On the "unpleasantness scale", "0" is represented as "not unpleasant" and "10" is represented as "the most unpleasant sensation imaginable."

Example instructions for intensity VAS – *“Please use the scale below to tell us how intense your pain is. Place an “X” on the scale that best describes the intensity of your pain.”*

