Mechanical pressure sensitivity assays^{10,12}: Assay involves determining the sensitivity threshold for painful pressure stimulation and then determining the quality and unpleasantness of that same pressure in a separate trial. Stimulation is provided with a standard clinical pressure algometer (see below instrument section). This device consists of a 0.5-2cm probe connected to a pressure meter. The probe is placed on the subject’s forearm or calf and pressure is gradually applied. Before the first training/experimental trial subjects will be allowed to apply the stimulus to themselves. During a trial, pressure will gradually be applied until the stimulus transitions from “innocuous pressure” to “painful pressure.” At this point, subject will say “stop” and the stimulus will be removed from the subject’s forearm/calf. When algometer is removed from the subject, the greatest pressure applied is automatically recorded in the device. This is the “pressure pain threshold” for the trial. 2 trials will be applied each to the forearm and calf in two distinct sites (on each limb) to avoid damage to a single area. After the pressure threshold has been determined for a subject, 1 additional trial on each limb will be applied (in a third testing site). In this trial, the subject will be asked to evaluate the intensity and unpleasantness of a pressure stimulus given for 3 seconds. This is done with a standard 0-10 visual analog scale (VAS). On the “intensity scale”, “0” is represented as “no pain” and “10” is represented as “the worst pain imaginable.” On the “unpleasantness scale”, “0” is represented as “not unpleasant” and “10” is represented as “the most unpleasant sensation imaginable.” During this trial, the experimenter will tell the subject that they are going to apply a painful stimulus to the subject and then ask the subject to evaluate that pain (on the two VASs). The exact stimulus will be matched to the subject’s pain threshold determined during the baseline trials (e.g. if baseline trials for forearm indicated a pressure threshold of 50 N then subject will be asked to evaluate the pain of that stimulus). During subsequent testing days (days 1, 3, 5, 6), the pressure pain threshold will be re-measured to determine if there is a change from baseline. For the intensity/unpleasantness testing, subjects will be tested on experimental days 1, 3, 5, 6 at their original baseline pressure threshold (from day 0) AND the threshold determined on each individual day. This will allow an analysis of change from baseline and pain at threshold for each experimental day.

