The collection of data has been described in detail under "Procedures". The primary outcome is a change in Quantitative Sensory Testing. This includes a series (8) of Quantitative Sensory Tests measured at baseline and at the completion of the 1-week intervention period. These tests are measured at two sites (calf and forearm). Significant differences between groups for 7 of the tests (per body site) will be identified using a one-way ANOVA comparing percent change from baseline (post-test (i.e. day 6)/baseline test (i.e. day 0)). Given the number of statistical tests that will be required for the primary outcome measurements, $p < 0.01$ will be utilized for each body site. An additional test for mechanical sensitivity will be measured at each site using a rank sum test at $p < 0.05$.

The secondary outcomes for this study include (1) HR during exercise, (2) Borg RPE before and after exercise and (3) testing "acute" effects of exercise on QST testing. HR during exercise and Borg RPE are measured to make sure that exercise causes a change in HR and/or perceived exertion. HR and Borg RPE data will be analyzed using percent change from start of exercise (post-exercise/pre-exercise) with two-way ANOVA for 3 treatment groups (3-day, 5-day, 10 day) across time (day 1, 3, 5) with an adjusted p value of $p < 0.03$. Control group will not be included in that analysis as HR was not measured on the control days and perceived exertion is at "0" on all days. For acute effects of exercise, participants were given 8 QST tests (on each forearm and calf) 5 min and 30 min after each exercise (or control session) on days 1, 3, and 5. Significant differences between groups for these tests (per body site) will be identified using a two-way MANOVA comparing percent change from baseline (post-exercise/baseline test (i.e. day 0)) across the three days (day 1, day 3, day 5) and at the 5 min and 30 min time QST measuring point. Given the number of statistical tests ($n=8$) that will be required for the QST secondary outcome measurements, $p < 0.01$ will be utilized for each body site.

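### The VAS pain ratings are to be analysed as day 6 divided by day 0, with no rule for a day 0 score of 0 and no use of day 0 as a covariate

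*Combined protocol and SAP*

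**What the plan says.** Section 8 describes the primary outcome thus: "This includes a series (8) of Quantitative Sensory Tests measured at baseline and at the completion of the 1-week intervention period". Each test is done at the calf and the forearm. Seven of the eight per site are compared between the four groups by "one-way ANOVA comparing percent change from baseline (post-test (i.e. day 6)/baseline test (i.e. day 0", at p < 0.01. The eighth, mechanical sensitivity, has a rank sum test. The secondary acute-effect analysis is a "two-way MANOVA comparing percent change from baseline (post-exercise/baseline test (i.e. day 0)) across the three days" and the 5- and 30-minute time points, so it has the same denominator. Heart rate and Borg RPE are divided by the pre-exercise value and are not part of this point.

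Section 8 does not name the eight tests, say what happens when day 0 is 0, or enter day 0 in a model.

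Section 3 describes the measures. For heat there is a withdrawal latency, plus intensity and unpleasantness ratings of a 3-second 45°C stimulus. For pressure there is a threshold, plus intensity and unpleasantness ratings at the "pain threshold determined during the baseline trials"; on later days ratings are also taken at that day's own threshold. Of the ratings, Section 3 says: "This is done with a standard 0-10 visual analog scale (VAS"). The value 0 stands for no pain, or for not unpleasant.

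**The concern.** A ratio to baseline needs a baseline that stays clear of zero. Heat latency and pressure threshold do. A VAS rating need not, and the plan's own description of the heat stimulus makes low ratings plausible: "45°C is a standard temperature that is the typical minimal stimulus necessary to feel thermal pain".

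The participants who feel least at day 0 would then either leave the primary comparison or dominate it. Which of these happens would be decided after the data exist, on a primary outcome with 10 to 15 people per group. The ratio may also waste information: the day 0 score is collected for everyone and could be used as a covariate without any division.

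**Working it through.** **1. Which tests are affected.** Apart from mechanical sensitivity, Section 3 describes two measures that are not VAS ratings (heat latency, pressure threshold) and four ratings with their own day 0 value (heat and pressure, intensity and unpleasantness). That identifies 2 + 4 = 6 of the seven ratio tests; four of the seven are VAS ratings. The seventh is not identifiable. If it is a rating at each day's new pressure threshold, its only possible denominator is the day 0 pressure rating.

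**2. What a zero does.** Percent change is (day 6 − day 0)/day 0 = ratio − 1, so ratio and percent change give the same F test and both fail at day 0 = 0. For one rating at one site, a zero removes 1 primary ratio and 3 days × 2 time points = 6 secondary ratios, seven in all. Near zero, a participant going from 0.1 to 1.0 has ratio 10, while one going from 4 to 2 has ratio 0.5.

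**3. Where a zero is plausible.** The rated heat stimulus is 45°C. For the radiant device Section 3 says: "The device is set so that typical withdrawal thresholds occur at approximately 10 seconds into the trial". It adds: "The temperature on the glass at this point is" about 47°C. It also gives 121°F, which is (121 − 32) × 5/9 = 49.4°C; both exceed 45°C. The devices differ, so this supports low heat ratings but gives no rate. Unpleasantness can also be 0 when pain is felt. Zero is less likely for pressure intensity, because that force is the one the participant has called painful.

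**4. How often.** The documents give no VAS mean, SD or correlation, so everything from here rests on assumptions: SD 1.5, marks read to 0.1, 60 participants.
- Floored normal: P(0) = Φ((0.05 − mean)/1.5). Any zero among 60: 1 − (1 − P)^60.
- Gamma with the same mean and SD: shape (mean/1.5)², scale 1.5²/mean.

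| Day 0 mean | Floored normal: P(0) | Any zero in 60 | Gamma: P(0) | Any zero in 60 |
|---|---|---|---|---|
| 2 | Φ(−1.30) = 9.7% | 99.8% | 0.2% | 13% |
| 3 | Φ(−1.97) = 2.5% | 78% | 0% | 0% |
| 5 | Φ(−3.30) = 0.05% | 3% | 0% | 0% |

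**5. Power.** There is no planned figure to reproduce: Section 5 gives 10 (goal 15) per group without effect size, SD, alpha or test. Simulation, 20,000 trials per cell: 15 per group, alpha 0.01, day 0/day 6 correlation 0.5-0.7, a 1.5-point drop in all three exercise arms, zeros dropped from the ratio.

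| Scores, day 0 mean | Ratio ANOVA | Raw ANCOVA |
|---|---|---|
| Floored normal, 2 | 30-58% | 71-87% |
| Floored normal, 3 | 36-66% | 72-90% |
| Floored normal, 5 | 50-80% | 71-90% |
| Gamma, 2 | 59-91% | 57-75% |
| Gamma, 3 | 71-95% | 70-89% |
| Gamma, 5 | 66-92% | 71-90% |

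Rank-based ANCOVA for the gamma rows gives 87-97%, 78-93% and 71-89%: ahead of the ratio at mean 2, mixed at means 3 and 5. At 10 per group the floored-normal figures are 19-39% against 44-62%, 23-47% against 46-67%, and 29-55% against 44-66%. The mean-2 rows are partly a floor case: Φ((0.05 − 0.5)/1.5) = Φ(−0.30) = 38% of exercise participants would score 0 on day 6.

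**6. Does the zero rule matter?** Two rules that touch only zeros are dropping them and setting them to 0.1. In the 1.5-point case they give different verdicts in about 24-29% (mean 2), 17-19% (mean 3) and 1% (mean 5) of floored-normal trials, and in under 1% of gamma trials.

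**7. Type I error** at nominal 1%: ratio 0.4-1.0%, raw ANCOVA 0.8-1.1%, rank ANCOVA 0.9-1.2%. Taking the smaller p-value of the two zero rules does not push the ratio clearly above 1%.

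**The case against.** The best defence is that the size of the problem comes from the assumed distribution. Participants mark an X on a line, so an exact zero needs a mark at its very end, and a stimulus just sufficient for pain could produce low but nonzero ratings. With gamma scores zeros almost vanish. The ratio does use baseline, it keeps its type I error, and at gamma mean 2 with correlation 0.7 it beats raw ANCOVA by about 91% to 75%. A 1.5-point drop at mean 2 is a 75% reduction in every exercise arm, which is a large effect to assume. That VAS ratings are among the seven tests is an inference.

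Most of this stands, and it limits the size of the claim. It does not remove the gap: a permitted value leaves a primary endpoint undefined, and no rule covers it. The inference about the tests is strong, because Section 3 offers only two other measures for seven places.

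A reader might go further in three ways that the documents do not support:
- That the ratio inflates false positives. The simulations show that it does not.
- That the secondary analysis treats a participant's six values as independent, with a badly inflated error rate. Section 8 names a MANOVA, which can take the six values as one response vector, and Section 3 describes a repeated-measures design. The wording is ambiguous, but independence is not stated.
- That the choice of zero rule changes the verdict in close to half of trials. This would need a rule that adds a constant to all scores, which alters every ratio and not only those with a zero baseline.

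**Conclusion.** The point holds for the VAS ratings, not for heat latency or pressure threshold. Confidence is high that the planned ratio is undefined at a day 0 score of 0 and that no rule covers this. Confidence in the size of the harm is moderate, because every distributional input is assumed.

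If ratings are low and roughly floored normal, zeros are near certain at mean 2 and likely at mean 3, the choice of zero rule can decide the result, and the ratio gives up much of the available power. If ratings are centred near 5, zeros hardly matter and the remaining cost is power. If ratings are skewed and strictly positive, zeros are rare, and for a fixed drop the ratio may lose nothing. This should be fixed before group results are seen; it does not make the trial invalid.

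**What to change.** In Section 8:
- List the eight tests, and state which pressure rating (at the day 0 force or at that day's threshold) is compared with day 0.
- Analyse each VAS test by ANCOVA: day 6 rating as outcome, group as factor, day 0 rating of the same test and site as covariate. Prespecify rank-based ANCOVA for skewed scores. Zeros then need no special rule.
- In the secondary sensory analysis, use the value itself as outcome with day 0 as covariate, keep the planned group, day and time-point factors, and state how each participant's six values are kept linked (a participant random effect or a within-participant covariance).
- Show percent change descriptively only, where day 0 is above 0.
- If the ratio is kept, name one zero rule before any group result is seen.

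The cost is Section 8 wording, new model code and one degree of freedom per primary model; no new data or participants are needed. Power may fall if scores are strongly skewed and only raw ANCOVA is used. The 0.80 power check at 10 per group in Section 5 must use the new model. Part of Section 8 is written in the past tense, so the change should be dated; if group results have already been seen, report the ratio ANOVA beside the new model.

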
Procedures: Following the screening and training session, subjects will be randomized to one of four conditions (Control, Low Frequency of Exercise, Moderate Frequency of Exercise, and High Frequency of Exercise) and scheduled for their exercise and data collection sessions (Figure 1). Subjects in the control group will be scheduled for three experimental sessions within a five-day period: Days 1, 3, and 5. Control subjects will complete all of the physical and sensory/pain tests following a 30-minute period of rest (no physical activity) on each of these days. These subjects will be set up in a private room with various reading materials during this time period. Subjects in the low frequency of exercise group will be scheduled for three exercise sessions within a five-day period: Days 1, 3, and 5. Subjects in the moderate frequency exercise group will be scheduled for five exercise sessions within a five-day period: Days 1-5. Subjects in the high frequency exercise group will be scheduled for ten exercise sessions within a five-day period: Days 1-5. For all subjects, physical and sensory/pain measures will be taken on exercise days 1, 3, and 5, 5 and 30 minutes after exercise, and also on Day 6 (no exercise).

Exercise Session

Subjects will arrive at the Health Science Exercise Physiology Lab on their scheduled exercise days. Sessions will be scheduled at the same approximate time each day to control for factors that may influence exercise performance. At the initiation of each exercise session, HR measures will be taken. At the initiation of the session on days 1, 3, and 5, pain measurement will be made using the 3 assays described in detail above. For each assay, pain will be individually defined on a 0-10 visual analog scale (VAS), a common scale used in human pain testing¹³. Each assay is safe and produces only mild escapable acute (<1 min) pain. Pain measurements will be completed on both the calf and volar non-dominant forearm for each subject. On days 2 and 4 for subjects in the moderate frequency and high frequency of exercise group, sensory and pain measures are not collected.

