PARQ and You will be used to determine if a participant is not healthy enough to participate in the study due to a presence of a heart conditions, chest pain, dizziness, joint problems, and drug use.

AHA/ACSM Health Fitness Facility Preparticipation Screening Questionnaire collects past medical history, current health issues, and cardiovascular risk factors that would indicate exclusion from participation.

Physical performance

For all conditions, we will evaluate daily normal physical activity and intensity with a pedometer.

The International Physical Activity Questionnaire long version¹⁴ (IPAQ-long) will be used to obtain estimates of weekly physical activity. Based on subjects' responses, the total energy

expenditure for participation in different physical activities can be calculated. The total energy expenditure is used to categorize subjects based on the amount of vigorous, moderate, or low intensity activity they engage in.

The Borg RPE scale¹⁵ is used to collect a subjective measure of fatigue. The Borg RPE scale ranges from 6 (no exertion at all) to 20 (maximal exertion). This scale is based on expected heart rate during minimal, moderate, and vigorous intensity exercise. A subject who rates their exertion level as a 12 on this scale is working at a moderate intensity and should have a heart rate of 120 beats per minute (12×10).

All exercise sessions will be monitored using two wireless cameras (Dropcam Wireless Video Camera) to avoid influence of social observation while continuing to monitor subject's performance and physiological measures (HR) of exercise. Video will be transmitted via a secure Wi-Fi signal to a university-owned laptop computer. Either a PI or graduate student will view the real-time video to ensure subject's safety and continued optimal performance. Video will be transmitted via secure wireless signal to ensure confidentiality.

Pain measures –As described above, the three tests are for tactile sensitivity, thermal pain, and pressure pain.

Cutaneous Stimulators –

For cutaneous mechanical sensation, we will use standard von Frey filaments (Touch Test Sensory Evaluators; North Coast Medical). These filaments (ranging from 0.008g to 1.0g) are used to measure threshold for sensation to innocuous stimulation. See above for full description of assay.

Radiant Heat –

For radiant thermal heat measurements, we will use a standard “Hargreaves” apparatus (IITC Thermal Stimulus Apparatus) (see image to right).

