Pressure Algometer –

For pressure pain testing, we will use a standard mechanical pressure algometer (Wagner Instruments).

Anxiety measures

All groups will be assessed for anxiety with questionnaire methods using the Social Interaction Anxiety Scale (SIAS)¹⁶. The SIAS measures anxiety with respect to social interactions. It is one of the more often-used self-report measures of social anxiety, with numerous evidence-based studies demonstrating its reliability and construct validity¹⁷. The SIAS contains 20 items which are rated from 0 (not at all characteristic or true of participant) to 4 (extremely characteristic or true of participant). Items are self-statements describing one's typical cognitive, affective, or behavioral reaction to a variety of situations requiring social interaction in dyads or groups (e.g., going to a party, talking to an attractive member of the opposite gender, expressing one's feelings).

5. Sample selection and size

Healthy adults will be recruited for participation in this study. The PAR-Q and You form and the AHA screening questionnaire will be administered during the screening process to determine whether potential subjects meet the inclusion/exclusion criteria.

Inclusion criteria include:

- Between age 18-40
 - Normal BMI (18.5-25)
 - HR 60 to 100
 - BP less than or equal to 140/90
- *HR and BP will be taken as part of the screening process to determine eligibility and also taken at the beginning of each exercise session.

Exclusion criteria include as indicated by the PAR-Q and You and AHA screening forms:

- Age less than 18 or greater than 40 years
- Cardiac, respiratory, neurological or musculoskeletal disease
- Acute pain
- Chronic pain condition
- Diabetes
- BMI ≥ 25.1 or ≤ 18.4
- Regular participation in high intensity athletic/sporting activities
- Sedentary
- Anxiety or depression disorders.
- Tape allergy
- Currently pregnant

A power analysis of pain outcome indicates that a minimum of 10 people/condition will be sufficient to detect statistical differences in our primary dependent variable (pain sensitivity), but to account for variability, our recruitment goal is 15 people/condition. When 10 participants per group have completed the study, a preliminary analysis will be conducted for statistical power, if we reach 0.80, recruitment will stop.

6. Recruitment of subjects

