The following demographic variables will be collected and compared between groups to further check against potential bias; age, handedness, body mass index (BMI), baseline heart rate (HR), baseline blood pressure (BP), baseline IPAQ-short, and STAI (state-trait anxiety). A significant difference in the proportion handedness will be tested using the Chi-Square test where a $p < 0.05$ will be considered significant. All other continuous variables will be tested using the one-way ANOVA to test for significance differences between the four study groups ($p < 0.05$).

9. Dissemination of Results

Results of this study will be submitted to a peer-reviewed journal for publication and will be available to the public.

10. Emphasize issues relating to interactions with subjects and subjects' rights

Subjects will be notified of their rights, all risks and benefits of participation in this study during the informed consent procedure. Subjects will be informed that they may withdraw from participation at any time. Data collection sessions will be scheduled at times that are mutually convenient for the subject and the researchers and all efforts will be made to work with the subject's schedule. All personal and health information will be kept confidential as data will be coded. Identifiers will be stored in a locked filing cabinet and all coded data will be stored in either a separate locked filing cabinet or a password protected computer. Only researchers and staff directly involved on this study will have access to this information. Health information obtained for this study will come directly from the participant and not their healthcare providers

or medical records. This information will be obtained during screening occurring in the Rangos School of Health Sciences exercise physiology lab and therefore is not under HIPAA.

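### Mechanical sensitivity, one of the eight primary sensory tests, is left at 0.05 without a reason, while the other seven primary tests, and all eight in the secondary analysis, are held to 0.01

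*Combined protocol and SAP*

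**What the plan says.** Section 8 defines the primary outcome as change in Quantitative Sensory Testing: "This includes a series (8) of Quantitative Sensory Tests measured at baseline" and again after the one-week intervention, at the calf and the forearm. Seven tests per site are compared across the four groups by one-way ANOVA of percent change from Day 0 to Day 6. Their threshold, set separately at each site, is explained: "Given the number of statistical tests that will be required for the primary outcome measurements, $p < 0.01$ will be utilized". The next sentence reads "An additional test for mechanical sensitivity will be measured at each site using a rank sum test at $p < 0.05". No reason is given for the different level.

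For the secondary acute-effects analysis, Section 8 counts eight sensory tests and again applies 0.01 per site because of that number. Mechanical sensitivity is not excepted there. Two other thresholds appear in Section 8: heart rate and Borg RPE are tested "with an adjusted p value of $p < 0.03", and baseline handedness is compared "using the Chi-Square test where a $p < 0.05$ will be considered significant". No familywise error rate and no named correction method appear anywhere.

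On what kind of measure mechanical sensitivity is, the text points both ways. Section 3 (Exercise Session) says "pain measurement will be made using the 3 assays described in detail above", and Section 4 (Pain measures) says "the three tests are for tactile sensitivity, thermal pain, and pressure pain". Section 5 names the primary dependent variable as pain sensitivity: "a minimum of 10 people/condition will be sufficient to detect statistical differences in our primary dependent variable (pain sensitivity"). Section 10 describes the filament stimulus as not painful.

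**The concern.** The plan tightens its primary threshold because there are many tests, then gives the loosest threshold to one of those same tests. Only seven of the eight go to ANOVA, so the mechanical sensitivity test must be the eighth; otherwise one primary test would have no analysis at all. The filaments deliver a fixed set of forces, which justifies a rank method but not a different alpha.

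What can count as a primary finding is at stake. A mechanical sensitivity result at, say, p = 0.03 would be significant under the primary rule but not under the rule that the plan uses for the same measure as a secondary outcome. The text does not settle whether such a result supports the primary conclusion, so that could be decided after the data are seen.

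**Working it through.** **Inputs.** Eight primary tests per site, two sites, seven ANOVAs at 0.01, one rank test at 0.05, and 0.01 for eight tests in the secondary analysis (all Section 8); four groups (Section 3); 10 per group minimum and 15 as the goal (Section 5).

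**Can 0.01 be reproduced?** Not exactly, because no method or overall level is stated. Bonferroni at an assumed 5% gives 0.05/7 = 0.0071 or 0.05/8 = 0.00625, and both become 0.01 at two decimals. Likewise 0.05/2 = 0.025 becomes the plan's 0.03. A 5% target is therefore a plausible inference and no more.

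**One family per site, independent tests.** The rate is 1 minus the product of (1 − alpha) over the tests.

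| Thresholds | Formula | Rate |
|---|---|---|
| Seven ANOVAs alone at 0.01 | 1 − 0.99^7 | 6.8% |
| As written | 1 − 0.99^7 × 0.95 | 11.45% |
| All eight at 0.01 | 1 − 0.99^8 | 7.73% |
| Seven at 0.00625, eighth at 0.05 | 1 − 0.99375^7 × 0.95 | 9.08% |
| All eight at 0.00625 | 1 − 0.99375^8 | 4.89% |

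**Where the excess comes from.** Above 5%, the excess is 11.45 − 5 = 6.45 points. Moving only mechanical sensitivity to 0.01 removes 11.45 − 7.73 = 3.7 points. Tightening only the seven to 0.00625 removes 11.45 − 9.08 = 2.4 points, and 2.4/6.45 = 37%. The 0.05 threshold is the larger contributor, but the rounding up to 0.01 supplies over a third.

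**Correlated tests.** The plan gives no correlations, so equal correlations of 0.3, 0.5 and 0.7 were assumed. Each setting used 60,000 simulated trials with no group effect, seven four-group ANOVAs and one Kruskal-Wallis test.

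| Setting | 0.3 | 0.5 | 0.7 |
|---|---|---|---|
| As written, normal, 15 per group | 10.4% | 9.5% | 7.8% |
| As written, normal, 10 per group | 10.5% | 9.7% | 7.9% |
| As written, lognormal (log SD 0.8), 15 per group | 9.1% | 8.2% | 7.4% |
| As written, lognormal (log SD 0.8), 10 per group | 8.7% | 8.1% | 7.1% |
| Seven ANOVAs alone, normal, 15 per group | 6.4% | 5.8% | 4.7% |
| All eight at 0.01, normal, 15 per group | 7.1% | 6.4% | 5.0% |

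Over log SD 0.6 to 1.0, the skewed results run from 6.9% to 9.6%.

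These settings assume that touch is as correlated with the pain tests as they are with each other. If touch were independent of them, the normal results with 15 per group would be 1 − (1 − 0.0638) × 0.95 = 11.1%, 1 − (1 − 0.0583) × 0.95 = 10.5% and 1 − (1 − 0.0467) × 0.95 = 9.4%.

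**Both sites together, 16 independent tests.** As written: 1 − (0.99^7 × 0.95)^2 = 21.6%. All at 0.00625: 1 − 0.99375^16 = 9.5%.

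**The case against.** The best defence is that mechanical sensitivity is a separate question. Section 8 calls it an additional test, Section 5 names pain sensitivity as the primary variable, and Section 10 says the stimulus is not painful. As two families, the seven pain tests run at about 5 to 7% and mechanical sensitivity at 5%, which is close to target. Every threshold is also fixed in advance and visible. This defence stands in part: the text permits it but never states it. Counting the measure in the primary eight, and holding it to 0.01 among the secondary eight, points the other way.

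Three stronger readings are tempting but unsupported.

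- A reader might infer that the plan breaches its own 5% familywise level by a factor of 2.3 (11.45/5). No such level is stated. The plan's own rule for eight sensory tests implies 7.7%, and against that the factor is about 1.5 (11.45/7.73).
- A reader might infer that the 0.05 threshold explains the whole excess. Correcting it alone still leaves 7.7% under independence.
- A rank sum test is ordinarily a two-group test, so a reader might infer uncorrected pairwise tests at 0.05. By simulation, mechanical sensitivity alone would then run at about 11 to 12% (three comparisons with control) or 18 to 19% (all six pairs). The plan specifies no pairwise comparisons, and the phrase may loosely mean one four-group rank test. The wording needs clearing up, but these figures should not be added to the size of the problem.

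Nor is the two-site 21.6% a breach of anything stated, because the plan sets its thresholds for each body site.

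**Conclusion.** The concern holds as an unexplained inconsistency in a decision threshold: the same measure is at 0.05 when primary and at 0.01 when secondary. The arithmetic under independence is exact. The correlated range of about 8 to 10.5% (about 7 to 10% if skewed) rests on assumed equal correlations and one four-group rank test. The excess exists only if the eight tests form one family per site. That is the more coherent reading of Section 8 but not the only one, and the 5% benchmark is inferred. The point should be fixed before analysis, because it determines whether a mechanical sensitivity result can count as a primary finding.

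**What to change.** In Section 8, do one of two things.

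1. Test mechanical sensitivity with one four-group rank test (Kruskal-Wallis) at p < 0.01, like the other seven. This matches the plan's own rule for eight tests and gives 7.7% per site if independent, or about 5 to 7% at correlations of 0.7 to 0.3.
2. State that it is not a pain test and make it secondary, still naming one four-group rank test.

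Optionally, if 5% per site is the intended familywise level, state it and use Holm at 0.05 over the eight tests (strictest step 0.00625) or, under option 2, over the seven (strictest step 0.0071). The simulated rate is then 4.6 / 4.2 / 3.3% or 4.7 / 4.3 / 3.4% at correlations 0.3 / 0.5 / 0.7 (normal data, 15 per group). This goes further than the documents require. In every case, say that conclusions are per site, since the two-site rate is higher.

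The cost is a few sentences, some power, and a recheck of the Section 5 power statement, which gives no alpha. Using an ANOVA approximation, an effect on mechanical sensitivity with 80% power at 0.05 keeps about 57% at 0.01 with 15 per group (56% with 10). At Holm's strictest step it keeps about 51% (49%), part of which Holm recovers when other tests are rejected. For the seven ANOVAs, option 1 costs nothing; at the 0.00625 step, an effect with 80% power at 0.01 keeps about 75%.
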